Schedule A: Lenalidomide will be administered orally at 20 mg total daily dose on days 1 to 21 of a 28 day cycle in patients with follicular and marginal zone lymphoma. Following cycle 3, if patients fail to show a response (partial or complete) the dose will be increased to 25mg/day. Patients with a diagnosis of small lymphocytic lymphoma (SLL) will begin at a dose of 10 mg total daily on days 1 to 21 of a 28 day cycle. This dose will be escalated by 5mg every 28 days up to 20mg if no toxicity is encountered. If no response is observed by cycle 3, the dose will be increased to 25 mg. (see dose modification for lenalidomide table). A single 375 mg/m2 intravenous dose of rituximab will be given at day 1 of every cycle.

Schedule B: Lenalidomide will be administered orally at 20 mg total daily dose on days 2 to 22 of a 28 day cycle in patients with follicular lymphoma. Following cycle 3, if patients fail to show a response (partial or complete) the dose will be increased to

25mg/day. Patients with a diagnosis of small lymphocytic lymphoma (SLL) will begin at a dose of 10 mg total daily on days 2 to 22 of a 28 day cycle. This dose will be escalated by 5mg every 28 days up to 20mg if no toxicity is encountered. If no response is observed by cycle 3, the dose will be increased to 25 mg. (see dose modification for lenalidomide table). A single 375 mg/m2 intravenous dose of rituximab will be given at day 1, 8,15, and 22 of cycle 1 and on day 1 of every subsequent cycle. In the absence of progression or toxicity, patients will remain on treatment for a total of 12 months. If patients attain a complete response following cycle 6 or 9, lenalidomide will be reduced to 10mg daily for the remaining cycles with the same dosing schedule of rituximab and lenalidomide as described above."

Patients that have documented clinical benefit and no evidence of progression of disease can remain on treatment for a total of 12 months. Treatment will be continued at the cycle 6 dose level with the same dosing schedule of rituximab and lenalidomide as described above.

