Lenalidomide, in healthy volunteers, is rapidly absorbed following oral administration with maximum plasma concentrations occurring between 0.625 and 1.5 hours post-dose. Co-administration with food does not alter the extent of absorption (AUC) but does reduce the maximal plasma concentration (Cmax) by 36%. The pharmacokinetic disposition of lenalidomide is linear. Cmax and AUC increase proportionately with increases in dose. Multiple dosing at the recommended dose-regimen does not result in drug accumulation.

Pharmacokinetic sampling in myelodysplastic syndrome (MDS) patients was not performed. In multiple myeloma patients maximum plasma concentrations occurred between 0.5 and 4.0 hours post-dose both on Days 1 and 28. AUC and Cmax values increase proportionally with dose following single and multiple doses. Exposure (AUC) in multiple myeloma patients is 57% higher than in healthy male volunteers.

Pharmacokinetic Parameters:

Distribution:

In vitro (¹⁴C)-lenalidomide binding to plasma proteins is approximately 30%.

Metabolism and Excretion:

The metabolic profile of lenalidomide in humans has not been studied. In healthy volunteers, approximately two-thirds of lenalidomide is eliminated unchanged through urinary excretion. The process exceeds the glomerular filtration rate and therefore is partially or entirely active. Half-life of elimination is approximately 3 hours.

Supplier(s)

Celgene Corporation will supply Revlimid® (lenalidomide) to study participants at no charge through the RevAssist® program. All physicians who prescribe lenalidomide for research subjects enrolled into this trial and all research subjects enrolled into this trial must be registered in and must comply with all requirements of Celgene's RevAssist® program.

Dosage form

Lenalidomide will be supplied as capsules for oral administration. The tablets are available in 5, 10, 15, and 25 mg capsule strengths.

Packaging

Lenalidomide will be shipped directly to the patient. Bottles will contain a sufficient number of capsules for one cycle of dosing.

Storage

Lenalidomide should be stored at room temperature away form direct sunlight and protected from excessive heat and cold.

Prescribing Information

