Lenalidomide (Revlimid®) will be provided to research subjects for the duration of their participation in this trial at no charge to them or their insurance providers. Lenalidomide will be provided in accordance with the RevAssist® program. Per standard RevAssist® requirements all physicians who prescribe lenalidomide for research subjects enrolled into this trial, and all research subjects enrolled into this trial, must be registered in and must comply with all requirements of Celgene's RevAssist® program. Prescriptions must be filled within 7 days. Only enough lenalidomide for one cycle of therapy will be supplied to the patient each cycle.

Unused study drug supplies

Patients should follow instructions for the return of study medication per the RevAssist® program. The RevAssist® Program will be used to return unused Revlimid by calling [name] who will collect the drug.

Screening and Eligibility

The Investigator is responsible for keeping a record of all subjects who sign an Informed Consent Form for entry into the study. All subjects will be screened for eligibility. Screening procedures are outlined in Section 2, Schedule of Study Assessments and unless otherwise specified, must take place within 30 days prior to initiation of therapy.

Approximately 110 of subjects with indolent non-Hodgkins lymphoma will be screened for enrollment and must meet the eligibility criteria below. Bone marrow biopsy can be performed up to 60 days prior to study entry.

Inclusion Criteria

Subjects must meet the following inclusion/exclusion criteria to be eligible for the study.

Inclusion criteria

- 1. Understand and voluntarily sign an informed consent form.
- 2. Age \geq 18 at the time of signing the informed consent form.
- 3. Able to adhere to the study visit schedule and other protocol requirements.
- 4. Untreated indolent non-Hodgkin's lymphoma stage III-IV including small lymphocytic lymphoma, marginal zone lymphoma, grade 1 or 2 follicular lymphoma (prior radiation for localized disease allowed).
- 5. At least one measurable lesion according to the International workshop standardized response criteria for non-Hodgkin's lymphomas (IWG) greater than 1.5cm.
- 6. ECOG performance status of ≤ 2 at study entry
- 7. Laboratory test results within these ranges:
 - Absolute neutrophil count $\geq 1.5 \times 10^9 / L^{\dagger\dagger}$
 - Platelet count $\geq 100 \times 10^9/L$
 - Serum creatinine $\leq 2.0 \text{ mg/dL}$

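### Entry limits renal function by serum creatinine alone and no dosing rule uses renal function, although most lenalidomide leaves by the kidney, so starting exposure is only loosely controlled

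*Combined protocol and SAP*

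**What the plan says.** Section 5, Metabolism and Excretion, reports for healthy volunteers that "approximately two-thirds of lenalidomide is eliminated unchanged through urinary excretion". On the mechanism it adds: "The process exceeds the glomerular filtration rate and therefore is partially or entirely active". Under Absorption: "Cmax and AUC increase proportionately with increases in dose". The same section notes: "Exposure (AUC) in multiple myeloma patients is 57% higher than in healthy male volunteers".

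Inclusion criterion 7 has one renal line, serum creatinine of at most 2.0 mg/dL. Criterion 2 sets a minimum age of 18 and no maximum.

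For follicular and marginal zone lymphoma on schedule A, Overall design says: "Lenalidomide will be administered orally at 20 mg total daily dose on days 1 to 21 of a 28 day cycle". Schedule B gives follicular patients the same 20 mg on days 2 to 22. These groups are 80 + 30 = 110 of the 155 planned patients. SLL patients start at 10 mg: "This dose will be escalated by 5mg every 28 days up to 20mg if no toxicity is encountered". They can therefore reach 20 mg in cycle 3. The next step depends on response: "Following cycle 3, if patients fail to show a response (partial or complete) the dose will be increased to 25mg/day".

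The dose-adjustment tables, the conditions for starting a new cycle and the dose-modification table cover blood counts, rash, arrhythmia, allergy, thrombosis, thyroid disorder and other drug-related non-hematologic toxicity of grade 3 or more. None uses creatinine or clearance. The Schedule of Study Assessments collects weight and creatinine at screening and repeats chemistry on days 8 and 22 of cycle 1 and in each cycle, but no creatinine value is tied to a dose action.

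**The concern.** If a drug is cleared largely by the kidney and its AUC is proportional to dose, a given dose produces higher exposure when renal clearance is lower. Serum creatinine is an indirect limit on that clearance, because the same value corresponds to quite different clearances at different ages, weights and sexes. The plan controls dose in 5 mg steps but has no entry or dosing rule that accounts for a difference in exposure that may be as large as one or more of those steps. Patients near the creatinine limit could begin at a materially higher exposure than others on the same nominal dose, before response or tolerance is known. That bears on the safety of those patients and on how the toxicity rate at 20 mg is read.

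**Working it through.** The documents give no clearance figure, so there is nothing of the plan's to reproduce. What follows is an illustration.

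**From the protocol:** creatinine limit 2.0 mg/dL; about two-thirds renal elimination; AUC proportional to dose; 20 mg start; AUC 57% higher in myeloma patients than in healthy men.

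**Assumed:** Cockcroft-Gault; ages, weights and sexes as shown; the two-thirds fraction applies at 100 mL/min; the non-renal third is constant. Renal drug clearance follows creatinine clearance either in full or by half. Active secretion makes this uncertain, and half is not a lower bound.

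**Step 1, clearance at 2.0 mg/dL.** CrCl = (140 − age) × weight / (72 × creatinine), × 0.85 for women.
- Extremes for ages 40–80 and 50–100 kg: woman 80 y, 50 kg, 60 × 50 × 0.85 / 144 = 17.7; man 40 y, 100 kg, 100 × 100 / 144 = 69.4 mL/min.
- Cross-check at ages 40–80: MDRD 24–37 and CKD-EPI 23–41 mL/min/1.73 m².

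**Step 2, exposure ratio at the same dose.** Against 100 mL/min:
- Full: 1 / (1/3 + 2/3 × CrCl/100)
- Half: 1 / (2/3 + 1/3 × CrCl/100)

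The second reference is a 64-year-old, 75 kg man with creatinine 1.0: 76 × 75 / 72 = 79.2 mL/min. His own ratios are 1.161 (full) and 1.075 (half), and the values above are divided by these.

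| Patient at 2.0 mg/dL | CrCl | Ref 100, full / half | Ref 79, full / half |
|---|---|---|---|
| Man 45 y, 90 kg | 59.4 | 1.37 / 1.16 | 1.18 / 1.08 |
| Man 64 y, 75 kg | 39.6 | 1.67 / 1.25 | 1.44 / 1.17 |
| Woman 64 y, 70 kg | 31.4 | 1.84 / 1.30 | 1.59 / 1.21 |
| Woman 75 y, 60 kg | 23.0 | 2.05 / 1.35 | 1.77 / 1.25 |

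The ratios run from 1.08 to 2.05, so 20 mg acts like about 22 to 41 mg.

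**Step 3, clearance below which 20 mg exceeds the exposure of 25 mg (ratio 1.25).**
- Reference 100: full (1/1.25 − 1/3) × 150 = 70; half (1/1.25 − 2/3) × 300 = 40 mL/min. Examples above: 4 of 4 and 3 of 4 (one of the three at 25.04 mg).
- Reference 79: about 53 and 23 mL/min. Examples above: 3 of 4 and 1 of 4 (the one at 25.04 mg).
- If the yardstick is 25 mg in myeloma patients and lymphoma patients do not share their higher AUC: 25 × 1.57 = 39.25 mg, ratio 39.25 / 20 = 1.96. Full (1/1.9625 − 1/3) × 150 = 26 mL/min; half gives a negative value, so never. Examples above: 1 of 4 and 0 of 4.

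**Step 4, effect of a 40 mL/min floor (reference 100).** The highest ratio at entry becomes 1/(1/3 + 2/3 × 0.4) = 1.67 (full) or 1/(2/3 + 1/3 × 0.4) = 1.25 (half). The highest among the examples without it is 2.05 or 1.35.

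**The case against.** The strongest reply is that the size is modelled, not observed. All four examples sit exactly at the creatinine limit, their characteristics are invented, and the upper figures need full scaling and a 100 mL/min reference. In the cited relapsed indolent lymphoma study the median age was 64 (range 54–82), so a reference near 79 mL/min is at least as fair and gives smaller ratios. This stands, and is why the range is shown across both references and both scalings.

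A reader might infer that patients near the limit start above a dose the plan regards as unsafe. The documents do not support that. The move from 20 to 25 mg is for patients without a response. The background describes 25 mg as a starting dose in indolent and aggressive lymphoma and in myeloma, with an acceptable safety profile reported in the indolent study. In the myeloma phase I studies, at doses up to 50 mg, the MTD was not reached within 28 days. The same text does report dose modifications for myelosuppression after day 28 at 25 and 50 mg, and Section 5 links 25 mg to more tumor flare and tumor lysis in CLL. The plan already starts SLL patients at 10 mg.

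There is also existing cover. Exclusion 3 lets the investigator refuse patients at unacceptable risk. Hematology is checked on days 8 and 22 of cycle 1, each cycle, and around day 14 of cycles 2–12. Low counts trigger holds and, on days 2–14, restart at the next lower level. Each cohort has a Bayesian toxicity rule assessed at the end of cycle 1. These measures are discretionary or act after toxicity. The cohort rule counts only grade 3–4 non-hematologic events, whereas falling neutrophils and platelets were dose-limiting in the myeloma studies. The cover reduces the concern without closing it.

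**Conclusion.** The gap is real: one creatinine limit, no clearance limit, and no renal dosing rule for a drug the protocol describes as about two-thirds renally excreted. Its size is uncertain. Under the stated assumptions, exposure at the same 20 mg is 8% to 105% above the reference in the four examples. Whether that passes the exposure of 25 mg depends on the scaling and the reference, and the documents settle neither. They show no harm and do not give the share of patients near the limit. It would be wrong to read the example clearances as a description of who will enrol, or the exposure ratios as a predicted toxicity rate. The point is worth acting on because a pre-dose safeguard costs little and the existing cover is discretionary or reactive.

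**What to change.** Calculate Cockcroft-Gault clearance at screening for every patient, record it, and extend the renal line of criterion 7 to: *serum creatinine of at most 2.0 mg/dL and estimated creatinine clearance of at least 40 mL/min*. Keep the creatinine ceiling, because 40 mL/min alone would admit the 45-year-old, 90 kg man up to 95 × 90 / (72 × 40) = 2.97 mg/dL.

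State that 40 is a judgement from an assumed model, to be confirmed by the sponsor's clinical pharmacology. It is the break-even under half scaling at a 100 mL/min reference. Under full scaling it still lets 20 mg act like 33 mg.

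The cost is one eligibility line and one derived variable, with no new test. Baseline clearance could also enter the logistic regression of toxicity on prognostic factors planned in Section 11.3. The downside is the loss of some older or low-weight patients. The effective creatinine ceiling becomes 1.98, 1.57 and 1.15 mg/dL in the last three examples, and an 80-year-old, 55 kg woman with creatinine 1.0 (60 × 55 × 0.85 / 72 = 39.0 mL/min) would be out.

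An alternative that keeps these patients is to admit those below the cut at the existing 10 mg level. At 23–40 mL/min, 10 mg acts like about 17–21 mg (full) or 12.5–13.5 mg (half) against 100 mL/min. Their cost is a lower starting dose. SLL patients already start at 10 mg, so this version must say whether the 5 mg per-cycle escalation applies to them. Neither version addresses a fall in renal function during treatment.

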Several phase II studies have shown activity with lenalidomide in CLL. Higher doses (25mg) have been associated with increased toxicity in the form of an increased incidence of tumor flare and tumor lysis syndrome (TLS).27,28 Tumor flare has also been correlated with response and may be associated with lenalidomide efficacy. 29 However, lower doses (10mg) appear to be better tolerated and have been associated with fewer cases of tumor flare. Ferrajoli et al treated 35 patients with CLL with a starting dose of 10mg daily for 28 days with a dose escalation to 25mg as tolerated. There were no cases of tumor lysis reported, and only 12% of patients developed tumor flare. The median dose level was 10mg. 30 In another phase II trial with lenalidomide in CLL, 2 out of the first 25 patients experienced TLS at the initial starting dose level (25mg). The study was modified to begin at a lower starting dose and none of the 16 patients who started on the 10mg dose level experienced tumor lysis. The incidence of tumor flare was unchanged, but the severity of reactions decreased significantly.31

Response to therapy will be assessed after 3 cycles and after 6 cycles of chemotherapy. In patients that continue on with extended dosing beyond cycle 6, response will also be evaluated after 9 and 12 cycles of chemotherapy. If after 3 cycles of therapy, there is stable disease without progression, as defined by IWG criteria, the lenalidomide dose will be increased for a total daily dose of 25mg, or 5 mg above the current dose in patients with SLL. If there is evidence of progression of disease, the patient will discontinue study medication.

The rationale for schedule B is derived from studies in both CLL and multiple myeloma suggest a clinical benefit (response rate and PFS) with extended dosing of lenalidomide. In schedule B, the dose of lenalidomide will be reduced in responding patients on cycles 7-12 to minimize potential myelosupression with increased exposure. In addition, significant infusion reactions to rituximab have been noted to occur beyond cycle 2. Although etiology of the infusion reactions is unknown, the severity of the reaction may be potentiated by concurrent dosing of lenalidomide. Ancedotal experience suggests that starting lenalidomide on day 2 of treatment (rituximab on day 1) may lessen the observed toxicity. Dose intensification of rituximab (weekly dosing) will occur in cycle 1 to increase mean serum concentration early in treatment.

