The amount of drug to be administered will be based on BSA. Body surface area will be calculated using a standard nomogram on Cycle 1, Day 1 and at subsequent visits if the subject experiences a >5% change in body weight from the weight used for the most recent BSA calculation.

Schedule A: The planned dose of lenalidomide for patients with follicular lymphoma and marginal zone lymphoma is 20 mg/day, orally on days 1-21 followed by 7 days rest (28 day cycle). Following cycle 3, if patients fail to show a response (partial or complete) the dose will be increased to 25 mg/day.

Schedule B: Lenalidomide will be administered orally at 20 mg total daily dose on days 2 to 22 of a 28 day cycle in patients with follicular lymphoma. Following cycle 3, if patients fail to show a response (partial or complete) the dose will be increased to

25mg/day. Patients with a diagnosis of small lymphocytic lymphoma (SLL) will begin at a dose of 10 mg total daily on days 2 to 22 of a 28 day cycle. This dose will be escalated by 5mg every 28 days up to 20mg if no toxicity is encountered. If no response is observed by cycle 3, the dose will be increased to 25 mg. (see dose modification for lenalidomide table). A single 375 mg/m2 intravenous dose of rituximab will be given at day 1, 8,15, and 22 of cycle 1 and on day 1 of every subsequent cycle. In the absence of progression or toxicity, patients will remain on treatment for a total of 12 months. If patients attain a complete response following cycle 6 or 9, lenalidomide will be reduced to 10mg daily for the remaining cycles with the same dosing schedule of rituximab and lenalidomide as described above.

Dosing will be at approximately the same time each day. The planned dose of lenalidomide for patients with SLL is 10 mg/day, orally on days 1-21 followed by 7 days rest (28 day cycle). If no toxicities are encountered, the dose of lenalidomide in patients with SLL will be increased by 5 mg with each cycle up to 20 mg/day. Following cycle 3, if patients fail to show a response (partial or complete) the dose will be increased to 25 mg/day. Only one cycle of study drug will be supplied to the patient each cycle.(for dose modification guidelines, see Table 2: Dose modification for Lenalidomide) Only one cycle of study drug will be supplied to the patient each cycle.

If a dose of lenalidomide is missed, it should be taken as soon as possible on the same day. If it is missed for the entire day, it should not be made up.

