If these conditions are not met on Day 1 of a new cycle, the subject will be evaluated weekly and a new cycle of lenalidomide will not be initiated until the toxicity has resolved as described above. If lenalidomide dosing was halted during the previous cycle and was restarted with a one-level dose reduction without requiring an interruption for the remainder of the cycle, then that reduced dose level will be initiated on Day 1 of the new cycle. If lenalidomide dosing was omitted for the remainder of the previous cycle or if the new cycle is delayed more than 7 days due to toxicity newly

encountered on the scheduled Day 1, then the new cycle will be started with a one-level dose reduction.

Instructions for dose modifications or interruption during a cycle.

Table 2: Dose Modificatio	n for Lenalidomide	
NCI CTC Toxicity Grade	Day 2-14 of Cycle	≥Day 15 of Cycle
Grade 3 neutropenia associated with fever (temperature ≥ 38.5° C) or Grade 4 neutropenia	 Hold (interrupt dose). Follow CBC weekly. If neutropenia has resolved to ≤ grade 2 restart at next lower dose level and continue the cycle until Day 21. 	Omit lenalidomide for remainder of cycle If neutropenia is the only toxicity for which a dose reduction is required. G-CSF may be used and the dose maintained for the next cycle at the investigators discretion.
Thrombocytopenia [†] ≥Grade 3 (platelet count < 50,000/mm³)	 Hold (interrupt dose). Follow CBC weekly. If thrombocytopenia resolves to ≤ grade 2 restart at next lower dose level and continue the cycle until Day 21. 	Omit lenalidomide for remainder of cycle
Non-blistering rash Grade 3	 If Grade 3 hold (interrupt) dose. Follow weekly. If the toxicity resolves to ≤ grade 1 prior to Day 21 restart at next lower dose level and continue the cycle until Day 21. 	Omit lenalidomide for remainder of cycle.
Grade 4	 Discontinue lenalidomide study drug. 	 Discontinue lenalidomide study drug.
Desquamating (blistering) rash- any Grade	 Discontinue lenalidomide study drug. 	Discontinue lenalidomide study drug.
Erythema multiforme ≥ Grade 3	 Discontinue lenalidomide study drug. 	Discontinue lenalidomide study drug.
Sinus bradycardia/ other cardiac arrhythmia Grade 2	 Hold (interrupt) dose. Follow at least weekly. If the toxicity resolves to ≤ grade 1 prior to Day 21 restart at next lower dose level and continue the cycle until Day 21. 	Omit lenalidomide for the remainder of the cycle.
≥ Grade 3	Discontinue lenalidomide study drug.	 Discontinue lenalidomide study drug.

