Allergic reaction or hypersensitivity Grade 2-3	 Hold (interrupt) dose. Follow at least weekly. If the toxicity resolves to ≤ grade 1 prior to Day 21 restart at next lower dose level and continue the cycle until Day 21. 	Omit lenalidomide for the remainder of the cycle.
Grade 4	Discontinue lenalidomide study drug.	Discontinue lenalidomide study drug

Table 2: Dose Modification	n for Lenalidomide	
NCI CTC Toxicity Grade	Day 2-14 of Cycle	≥Day 15 of Cycle
Venous thrombosis/embolism ≥ Grade 3	 Hold (interrupt) dose and start anticoagulation; restart at investigator's discretion (maintain dose level). 	Omit lenalidomide for remainder of cycle. Anticoagulation measures as described in Conncomitant therapy section below.
other non-hematologic toxicity assessed as Lenalidomide-related ≥ Grade 3	 Hold (interrupt) dose. Follow at least weekly. If the toxicity resolves to ≤ grade 2 prior to Day 21 restart at next lower dose level and continue the cycle until Day 21. 	Omit lenalidomide for remainder of cycle.
Hyperthyroidism or hypothyroidism	Omit lenalidomide for remainder of cycle, evaluate etiology, and initiate appropriate therapy. Restart lenalidomide next cycle (decrease dose by one dose level).	Omit lenalidomide for remainder of cycle, evaluate etiology, and initiate appropriate therapy. Restart lenalidomide next cycle (decrease dose by one dose level).

[†] If patient had low baseline platelets due to prior to study entry, dose reduction not required.

Dose Escalation

In schedule B, all patients in a complete response will reduce lenalidomide to 10mg daily on cycles 7-12.

If after 3 cycles of therapy, there is stable disease without evidence of progression as defined by IWG criteria, the lenalidomide dose will be increased to 25 mg per day (dose level +1) or 5 mg above the current dose in patients with SLL. The initiation of the next cycle will only be initiated if there is no evidence of toxicity as outlined above in the Instructions for Initiation of a New Cycle.

Treatment compliance

Subjects will be asked to maintain a diary to record the drug administration.

Prohibited concomitant therapy

Concomitant use of sargramostim (GM-CSF), other anti-cancer therapies, including radiation, thalidomide, or other investigational agents is not permitted while subjects are receiving study drug during the treatment phase of the study.

Discontinuation of Study Treatment

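### For SLL patients without a response after cycle 3 the protocol gives two incompatible lenalidomide doses: a fixed 25 mg, and 5 mg above the current dose

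*Combined protocol and SAP*

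**What the plan says.** All of the relevant text is in Section 5.

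- **SLL titration.** SLL patients start at 10 mg. Overall design then says: "This dose will be escalated by 5mg every 28 days up to 20mg if no toxicity is encountered".
- **SLL step after cycle 3, fixed.** Overall design, for both schedules, says: "If no response is observed by cycle 3, the dose will be increased to 25 mg". Drug Administration repeats this under Schedule B. Its separate SLL paragraph uses the sentence that also serves follicular and marginal zone patients: "Following cycle 3, if patients fail to show a response (partial or complete) the dose will be increased to 25 mg/day".
- **SLL step after cycle 3, relative.** The response-assessment paragraph of Overall design says that, with stable disease, "the lenalidomide dose will be increased for a total daily dose of 25mg, or 5 mg above the current dose in patients with SLL". The Dose Escalation paragraph agrees: "the lenalidomide dose will be increased to 25 mg per day (dose level +1) or 5 mg above the current dose", the last alternative being for SLL.
- **Follicular and marginal zone step.** Every statement gives 25 mg. Dose Escalation labels it dose level +1, which Table 1 defines from a 20 mg start.
- **Starting a new cycle.** Dose Escalation allows the next cycle only with "no evidence of toxicity as outlined above in the Instructions for Initiation of a New Cycle". That earlier section says that after a hold and a one-level reduction in the previous cycle, "then that reduced dose level will be initiated on Day 1 of the new cycle". After dosing was omitted for the rest of a cycle, or after a toxicity delay of more than 7 days, "then the new cycle will be started with a one-level dose reduction".

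**The concern.** Two physicians could give the same SLL patient different doses in cycle 4 and both be following the protocol. The protocol has a reason to care about this. Overall design reports that 25 mg in CLL was associated with more tumor flare and tumor lysis, and SLL patients therefore start at 10 mg and climb in 5 mg steps. A jump from 10 to 25 mg skips that titration.

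Safety and uniform dosing from cycle 4 onward are at stake, and with them the later adverse event data and the responses assessed after cycles 6, 9 and 12. The monitored outcomes are not affected. Section 10 assesses toxicity at the end of cycle 1 and response at the end of cycle 3, both before this step. For the same reason, the toxicity stopping rule could not detect harm caused by the step.

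**Working it through.** The plan states no figure to reproduce. The check compares the texts and applies each rule to the dose ladder.

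**1. Do the two rules reach the same patients?** The fixed text is triggered by no partial or complete response, the relative text by stable disease. Patients who progress discontinue drug (Overall design), so a non-responder who continues is in effect a patient with stable disease. The rules address the same patients.

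**2. What dose does each rule give?** Inputs are the SLL levels in the table of dose adjustment steps for SLL (5, 10, 15, 20 and 25 mg daily for 21 days of 28). Relative dose = current dose + 5 mg. Fixed dose = 25 mg. Gap over the dosing days = (25 − relative dose) × 21.

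| SLL dose in cycle 3 | Fixed text | Relative text | Gap over 21 dosing days |
|---|---|---|---|
| 20 mg | 25 mg | 20 + 5 = 25 mg | (25 − 25) × 21 = 0 mg |
| 15 mg | 25 mg | 15 + 5 = 20 mg | (25 − 20) × 21 = 105 mg |
| 10 mg | 25 mg | 10 + 5 = 15 mg | (25 − 15) × 21 = 210 mg |
| 5 mg | 25 mg | 5 + 5 = 10 mg | (25 − 10) × 21 = 315 mg |

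The lowest active SLL level (5 mg for 14 days) is left out because the relative text does not say how many days would apply after the rise.

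**3. Who is below 20 mg in cycle 3?** Undisturbed titration gives 10, 15 and 20 mg in cycles 1, 2 and 3. Since each rise requires that no toxicity was encountered, a patient below 20 mg in cycle 3 is mainly one whose titration was stopped or reversed for toxicity. The rules agree for the patient who tolerated the drug and differ for the one who did not.

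**4. Does another rule settle it?**

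- Two tables carry the number 2. The SLL ladder lists levels but does not say when to move up. The dose-modification table covers holds, reductions and discontinuation and has no re-escalation rule.
- The new-cycle criteria decide whether a cycle may start. Most related events need only be at grade 2 or lower.
- The carry-forward rule covers a reduction in the cycle just completed. Take an SLL patient cut from 15 to 10 mg during cycle 3: carry-forward gives 10 mg in cycle 4, the relative text 15 mg and the fixed text 25 mg. No sentence says which prevails.

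**5. Follicular and marginal zone patients.** The texts do not contradict each other. A patient reduced in cycle 1 or 2 who then completes cycle 3 without further toxicity is simply not addressed.

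**The case against.** The strongest defence is that the fixed sentence describes the default path. In Overall design and in the Schedule B text it is followed at once by a pointer to the dose-modification table, and Drug Administration sends patients with adverse events to Table 2. On the default path of 10, 15 and 20 mg, the next dose is 25 mg under either rule. The Dose Escalation paragraph, which is the dedicated text, gives the relative rule. The trial is also run at a single institution, which reduces the scope for divergent practice. This shows what was probably intended, but the table pointed to contains nothing on going back up, so the contradiction stands for a patient below 20 mg.

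A reader might infer more for follicular and marginal zone patients: that someone reduced for toxicity is ordered to 25 mg, above a 20 mg dose that was not tolerated. The documents do not support that. The label dose level +1, defined from 20 mg, can be read as presupposing a patient still on 20 mg, and the text is silent on one who is not. Nor does every reduction show intolerance of the dose: the table also orders a one-level reduction for hyper- or hypothyroidism, with treatment and then resumption.

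A reader might also conclude that a toxicity-reduced patient must never be re-escalated. That is a debatable clinical choice which the documents do not impose.

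**Conclusion.** For SLL the protocol is wrong as written: it states two incompatible doses after cycle 3, up to 15 mg a day apart on the 21-day levels, and nothing resolves them. For follicular and marginal zone patients there is an unaddressed case, which is the lesser point.

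The number of patients affected is likely to be small and cannot be computed, because the documents give neither a stable-disease rate nor a dose-reduction rate over three cycles. A reader might take the expected SLL non-responders, 45 × (1 − 0.60) = 18 at the planned response rate, as the count. That would be wrong: the 18 include patients who progress and stop, and patients at 20 mg, for whom the rules agree.

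The CLL tumor lysis figures in Overall design concern starting doses. They explain the cautious SLL titration but do not measure the risk of reaching 25 mg in cycle 4.

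The conclusion rests on reading the current text literally and on the SLL ladder as printed. No sample size, stopping boundary or monitored cycle-3 response figure changes.

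**What to change.** 1. In Overall design and Drug Administration, replace the fixed 25 mg for SLL with 5 mg above the current dose, maximum 25 mg. This is the rule already given in the response-assessment paragraph and under Dose Escalation.
2. State that the reduction rules for starting a new cycle take precedence over the step after cycle 3.
3. For follicular and marginal zone patients, state that the step to 25 mg applies only to those still on 20 mg. Leave it to the investigators to specify whether and how a reduced patient may be re-escalated.

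The cost is a wording amendment with its usual review, and no extra patients or procedures. The downside is that some patients without a response will not reach 25 mg.
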